### **Exclusion Criteria**

- pregnant women <18 years old or over 45 years old
- a urine dipstick urine with >2+ protein
- blood pressure >140/80 mmHg; hematocrit <30%
- refusal to take insulin
- inability to understand instructions or to consent to participate.

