### **Inclusion Criteria**

- Pregnant and at least 13 weeks gestation
- Diagnosed with gestational diabetes
- Failed diet therapy

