## **METHODS**

Subjects will be randomized 1:1 to receive usual insulin treatment of six injections daily (Humalog® injected three times daily before meals plus Humulin N® insulin injected at 8am, 4pm and midnight) as diagrammed in Figure 1, or 3 injections of Humalog® Mix50/50™ (injected only before meals) as diagrammed in Figure 2.

Baseline measures will include glucose tolerance test data, height, weight, and A1C by DCA2000+. In addition to the standard instruction to test blood glucose pre- and one-hour postprandial, all participants will be asked to test blood glucose levels at 3 a.m. Patients on the Humalog® Mix50/50™ arm of the study will be initially prescribed insulin doses of 0.3 times their weight in kilograms to be taken before each of three meals. Those on the standard therapy arm will be initially prescribed insulin doses calculated at 0.15 times their weight in kilograms for each of their 6 injections.

---

 We shall use American Diabetes Association criteria for diagnosis of GDM: blood glucose concentration >140 mg/dL one hour after administration of a 50 gram glucose load, followed by an oral glucose tolerance test (OGTT) in which 2 or more of the readings are at or above 95 mg/dL fasting, 180 mg/dL at one hour, 155 mg/dL at 2 hours and 145 mg/dL 3 hours after administration of a 100 gram glucose load (12).

Participants will be seen weekly for adjustment in dosages based on their food records, downloaded glucose monitor data and A1 C levels. Subjects in the study group whose fasting glucose exceeds 90 mg/dl will be prescribed Humalog® Mix75/25™ at their evening meal rather than Humalog® Mix50/50™. Subjects will be discontinued from the study if their 3 a.m. blood glucose concentration falls below 55 mg/dL that is unresponsive to a snack at bedtime or if their fasting blood glucose is greater than 90mg/dL despite increasing doses of Humalog® Mix50/50™ at the evening meal followed by treating with Humalog® Mix75/25™ at the evening meal.

Maternal weight will be recorded at each visit. Participants will be asked to bring their supply of insulin pens to every other visit, for which they will be paid ten dollars to maximize cooperation with this essential aspect of the research. The insulin pens will be counted as measures of adherence.

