## **SAMPLE SIZE**

40 women will be recruited into the study in order to achieve at least 30 evaluable subjects (15 in each treatment arm) over the 12 months duration of the study. Based on the standard deviation for fasting glucose concentrations reported from the NHANES II study, measurable data from 30 subjects (15 in each group) will have 80% power to find an inter-group difference as small as 8 mg/dL at a p-value of 0.05 (13).

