## **SECONDARY EFFICACY MEASURES**

The maternal A1C will be measured by Bayer DCA2000+ at baseline and at end of protocol. The 3 a.m. glucose records will be assessed for nocturnal hypoglycemia. Maternal weight gain will be assessed as an indicator of over-insulinization. In addition, we will analyze baby birth weight percentile, APGAR scores, cord blood insulin levels and mode of delivery as measures of fetal outcome. We will use insulin pen count data as an indicator of maternal adherence to the therapy regimen.

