## **STATISTICAL ANALYSIS**

Data analysis will be done using SAS for Windows version 9. Differences between groups in continuous variables (glucose, A1C, birth weight etc.) will be compared with t-tests and potential confounders (age, race/ethnicity etc.) will be controlled for with linear regression. Differences in categorical variables (hypoglycemic events, macrosomia, type of delivery

etc.) will be evaluated using chi-square or Fisher's tests as appropriate. Our tests will be testing the hypothesis that the two treatments are different and the null hypothesis will be equivalence.

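### Enrolment is not limited to singleton pregnancies, so a single twin pregnancy can add noise and chance imbalance to the secondary neonatal and weight-gain comparisons in arms of about 15

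*Protocol*

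**What the plan says.** **Eligibility.** The protocol's Inclusion Criteria admit a woman who is "Pregnant and at least 13 weeks gestation", has gestational diabetes and did not succeed on diet therapy. The Exclusion Criteria have five bullets: age ("pregnant women <18 years old or over 45 years old"), urine protein, blood pressure or hematocrit, refusal of insulin, and inability to understand or consent. Neither list mentions singleton, twin or multiple pregnancy, and nor does any other section.

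**Outcomes exposed.** Neonatal outcome is the second of the Secondary Objectives. Under Secondary Efficacy Measures, "we will analyze baby birth weight percentile, APGAR scores, cord blood insulin levels and mode of delivery as measures of fetal outcome". The same section treats maternal weight gain as a marker of too much insulin. The birth-data paragraph that closes Methods collects sex, length, birth weight, gestational week and mode of delivery, worded for one infant per birth.

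**Analysis.** Under Statistical Analysis, "Differences between groups in continuous variables (glucose, A1C, birth weight etc.) will be compared with t-tests". Categorical outcomes, including macrosomia and type of delivery, get chi-square or Fisher's tests. Linear regression adjusts for confounders, with age and race/ethnicity as the named examples. The unit of analysis for neonatal outcomes is not stated.

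**Size.** Under Sample Size, "40 women will be recruited into the study", with the aim of 30 evaluable, 15 per arm. Methods gives 1:1 randomization and mentions no stratification.

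**The concern.** A twin pregnancy can change birth weight, mode of delivery and maternal weight gain for reasons that have nothing to do with the insulin regimen. In a large trial such pregnancies roughly balance. Here one woman is 1/15 = 6.7 percentage points of an arm's delivery-mode result, and a single twin pregnancy has to sit in one arm or the other. Low twin weights could hide macrosomia in that arm, and extra maternal gain could be misread as over-treatment with insulin.

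An analysis plan can say how twins are analysed. It cannot undo their enrolment, and setting a woman aside afterwards costs an arm that has about 15 to begin with. Eligibility is fixed in the protocol, so the gap belongs there.

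**Working it through.** **The plan's own figure.** Sample Size claims "80% power to find an inter-group difference as small as 8 mg/dL at a p-value of 0.05" with 15 per arm. No SD is printed, so the claim can be back-solved but not verified. With the normal approximation, SD = 8 × √(15/2) / (1.960 + 0.842) ≈ 7.8 mg/dL two-sided; the exact t calculation gives about 7.5. This figure concerns maternal fasting glucose. The point made here does not touch it, and the proposed change leaves it as it is.

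**Inputs from the protocol.** 40 women recruited; 30 evaluable; 15 per arm; 1:1 allocation.

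**Assumptions, none of them in the documents.** Multiple-pregnancy rate p = 1–4%; each twin 600–1000 g lighter than a singleton; birth-weight SD 500 g; within-pair correlation 0.5–0.7.

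**Step 1. Chance of at least one multiple pregnancy, 1 − (1 − p)^n.**

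| p | given arm of 15 | 30 evaluable | 40 recruited |
|---|---|---|---|
| 1% | 14% | 26% | 33% |
| 2% | 26% | 45% | 55% |
| 3% | 37% | 60% | 70% |
| 4% | 46% | 71% | 80% |

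The column for 30 evaluable women is the relevant one, because the analysis is expected to rest on them.

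**Step 2. Standard error of the difference in mean birth weight.** 500 × √(2/15) = 183 g.

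**Step 3. Shift in one arm's mean from one twin pregnancy.**

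- One averaged value per woman (15 values): 600/15 = 40 g to 1000/15 = 67 g. Divided by 183 g, this is 0.22–0.37 standard errors.
- Both infants as separate rows (14 + 2 = 16 rows, of which the pair is 12.5%): 2 × 600/16 = 75 g to 2 × 1000/16 = 125 g. Divided by 183 g, this is 0.41–0.68 standard errors.

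With an SD of 400 g the two ranges become 0.27–0.46 and 0.51–0.86. With an SD of 600 g they become 0.18–0.30 and 0.34–0.57.

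**Step 4. Type I error.** An unpaired t-test was simulated 100,000 times per setting, with no treatment effect and one correlated twin pair in one arm. At a nominal two-sided 5%, rejection was 6.1–7.1% when both twins were separate rows, and 4.9–5.0% with one averaged value per woman.

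**The case against.** Much of the case on the other side stands.

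- **Double counting.** A reader might infer that twins will enter the tests as two independent observations. The protocol does not say so. It never states the unit of analysis, and a SAP that is not shown could set one value per woman. In that case the shift falls by about half and the type I error stays near 5%. Mode of delivery and maternal weight gain are in any case normally one value per woman, so for them the issue is plurality as a prognostic factor, not double counting.
- **Bias.** A reader might infer that the treatment comparison is biased. Allocation is randomized 1:1, so a twin pregnancy is as likely to fall in either arm. What remains is added variance and chance imbalance within the one trial that is run.
- **An internal contradiction.** The birth data are worded in the singular, but that is grammar and not a rule; the same paragraph also uses the plural for neonates. It does not conflict with the eligibility lists.
- **Scale.** These are secondary outcomes without a power calculation. With a standard error of 183 g, the difference detectable with 80% power is about 2.8 × 183 ≈ 510 g, so a shift of 40–125 g is small beside it.
- **Grams versus percentile.** The named measure is birth weight percentile. If the reference is specific to gestational age, which the protocol does not say, part of the twin deficit drops out. Statistical Analysis does name birth weight itself, so the gram figures are relevant, but no effect on the percentile has been calculated.
- **Adjustment.** The list of confounders is open-ended, so plurality could be added for continuous outcomes. It is not named.

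None of this answers the basic point: as written, the criteria admit twin pregnancies, and nothing in the protocol deals with them.

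**Conclusion.** The point holds as a minor one, limited to secondary outcomes. The eligibility criteria do not require a singleton pregnancy, and the protocol compares neonatal outcomes and maternal weight gain between small arms without accounting for plurality.

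The distortion is moderate and conditional. There is roughly a one-in-four to seven-in-ten chance that it arises at all among the evaluable women. If it does, the shift is 0.2–0.4 standard errors with one value per woman, or 0.4–0.7 with both infants as rows, which the protocol neither states nor rules out. Every one of these figures rests on the assumed twin rate, weight deficit and SD; the type I error also depends on the assumed within-pair correlation. The effects on delivery mode, weight gain, macrosomia and cord insulin were not quantified beyond the weight of one woman in an arm.

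It would go too far to say that the neonatal comparison is invalid, that it is biased, or that the primary fasting-glucose comparison is harmed.

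**What to change.** Add singleton pregnancy to the Inclusion Criteria, or multiple gestation to the Exclusion Criteria. One line is enough.

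The cost is small: 40 × 1% to 40 × 4% = 0.4 to 1.6 otherwise eligible women, or roughly one in 40. The stated sample size and power do not change.

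If the team prefers to keep multiple pregnancies eligible, the alternative is to state in advance that neonatal outcomes are analysed in singletons only, or with one value or cluster per mother. Averaging or clustering deals with double counting, but it leaves the chance imbalance in place.

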## **METHODS**

Subjects will be randomized 1:1 to receive usual insulin treatment of six injections daily (Humalog® injected three times daily before meals plus Humulin N® insulin injected at 8am, 4pm and midnight) as diagrammed in Figure 1, or 3 injections of Humalog® Mix50/50™ (injected only before meals) as diagrammed in Figure 2.

Baseline measures will include glucose tolerance test data, height, weight, and A1C by DCA2000+. In addition to the standard instruction to test blood glucose pre- and one-hour postprandial, all participants will be asked to test blood glucose levels at 3 a.m. Patients on the Humalog® Mix50/50™ arm of the study will be initially prescribed insulin doses of 0.3 times their weight in kilograms to be taken before each of three meals. Those on the standard therapy arm will be initially prescribed insulin doses calculated at 0.15 times their weight in kilograms for each of their 6 injections.

---

 We shall use American Diabetes Association criteria for diagnosis of GDM: blood glucose concentration >140 mg/dL one hour after administration of a 50 gram glucose load, followed by an oral glucose tolerance test (OGTT) in which 2 or more of the readings are at or above 95 mg/dL fasting, 180 mg/dL at one hour, 155 mg/dL at 2 hours and 145 mg/dL 3 hours after administration of a 100 gram glucose load (12).

Participants will be seen weekly for adjustment in dosages based on their food records, downloaded glucose monitor data and A1 C levels. Subjects in the study group whose fasting glucose exceeds 90 mg/dl will be prescribed Humalog® Mix75/25™ at their evening meal rather than Humalog® Mix50/50™. Subjects will be discontinued from the study if their 3 a.m. blood glucose concentration falls below 55 mg/dL that is unresponsive to a snack at bedtime or if their fasting blood glucose is greater than 90mg/dL despite increasing doses of Humalog® Mix50/50™ at the evening meal followed by treating with Humalog® Mix75/25™ at the evening meal.

Maternal weight will be recorded at each visit. Participants will be asked to bring their supply of insulin pens to every other visit, for which they will be paid ten dollars to maximize cooperation with this essential aspect of the research. The insulin pens will be counted as measures of adherence.

Consent forms of enrolled patients will be given to the hospital at prenatal enrollment and will be part of their hospital medical chart at the time of delivery. Delivery room nurses will be instructed to collect cord blood and notify the study coordinator of the birth. Data collected from the birth will include sex of the baby, gestational week, ethnicity, length, birthweight and mode of delivery. Neonates will be assessed for macrosomia and hypoglycemia. Maternal postpartum glucose levels will be recorded.

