**PROTOCOL**  
**HUMALOG® MIX50/50™ FOR THE TREATMENT OF INSULIN REQUIRING**  
**GESTATIONAL DIABETES**

**RATIONALE**

Controlling hyperglycemia during pregnancy decreases the risk of adverse neonatal and maternal outcomes. Not only must fasting glucose be normalized, but clinical evidence also indicates that controlling postprandial hyperglycemia will significantly reduce the risk of adverse neonatal and maternal outcomes (1-2).

Standard therapy to achieve near-normal glycemia in gestational diabetes involves combining intermediate-acting basal (NPH) insulin with rapid-acting insulin (insulin lispro), thereby requiring 6 daily injections (Figure 1). Premixed Humalog® Mix50/50™ has the potential advantage over combination rapid-acting plus NPH insulin because it involves fewer injections, and those injections are associated with mealtime (Figure 2). The potential downside to the premixed formulation is nocturnal hypoglycemia associated with the time lag between the dinner and breakfast dose. This study will evaluate the efficacy and safety of Humalog® Mix50/50™ compared to that of Humalog® plus Humulin N® insulin for the treatment of insulin-requiring patients with gestational diabetes mellitus, while monitoring glucose control, intrauterine growth and assessing pregnancy outcomes.

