## **SECONDARY OBJECTIVES**

1. Compare incidence of maternal hypoglycemic events between the two treatment arms.
2. Compare neonatal outcomes between the two treatment arms.
3. Compare fetal fat measurements between the two treatment arms.
4. Compare adherence rates and patient acceptability of the two injection regimens
5. Compare A1C between groups at end of protocol and within groups at baseline versus end of protocol.

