## **PRIMARY EFFICACY MEASURES**

The primary measure used to substantiate the primary study objective will be maternal glucose control as reflected by fasting values from glucose monitor data.

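### Only the Mix arm can leave the study on fasting glucose, the primary outcome, and the protocol does not say that follow-up continues after exit

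*Protocol*

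**What the plan says.** One sentence in METHODS gives two grounds for leaving the study.

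- **3 a.m. glucose.** "Subjects will be discontinued from the study if their 3 a.m. blood glucose concentration falls below 55 mg/dL that is unresponsive to a snack". This ground is not worded for one arm, and all participants test at 3 a.m.
- **Fasting glucose.** A woman also leaves if her "fasting blood glucose is greater than 90mg/dL despite increasing doses of Humalog® Mix50/50™ at the evening meal followed by treating with Humalog® Mix75/25™". The step before this exit is written for the Mix arm only: "Subjects in the study group whose fasting glucose exceeds 90 mg/dl will be prescribed Humalog® Mix75/25™ at their evening meal". No fasting exit is given for the six-injection arm.

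The primary measure (PRIMARY EFFICACY MEASURES) is "maternal glucose control as reflected by fasting values from glucose monitor data". One secondary objective is to "Compare A1C between groups at end of protocol and within groups at baseline versus end of protocol".

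On data that exist before exit, METHODS says: "Participants will be seen weekly for adjustment in dosages based on their food records, downloaded glucose monitor data". The same sentence goes on to list A1C levels. Birth data are arranged through the hospital chart from prenatal enrolment. SAMPLE SIZE says "40 women will be recruited into the study in order to achieve at least 30 evaluable subjects", and evaluable is not defined.

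**The concern.** The fasting ground requires that two premix steps have failed. A woman on separate lispro and NPH never receives a premix, so she cannot meet it however high her fasting glucose stays. Exit on this ground therefore happens in one arm only, and its trigger is the primary outcome.

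The wording takes her out of the study rather than off the assigned insulin, and the protocol provides for no later fasting readings or end-of-protocol A1C. If that is what happens in practice, the Mix women still observed late in the trial are partly selected for good fasting control, while the comparator women are not. The arms are then no longer comparable by randomisation. A later analysis plan can choose how to treat the gap, but it cannot supply readings the study did not collect.

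**Working it through.** **1. Reproducing the planned power.** SAMPLE SIZE gives 15 per arm, 8 mg/dL, 80% power and p = 0.05. The SD is not printed, so the 80% cannot be confirmed, only solved backwards. For a two-sided t-test (28 df) the noncentrality is 8 / (SD × √(2/15)). Power of 80% needs 2.90, so SD = 7.55 mg/dL. The normal approximation gives 8 / (2.802 × 0.365) = 7.82. Recruiting 40 for 30 evaluable allows 25% loss: 30 / 0.75 = 40, or 5 of 20 per arm.

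**2. Assumed inputs.** SD 7.55; 20 women per arm; control mean μ of 80, 82 or 85 mg/dL; true Mix excess 8 mg/dL. The documents give no control mean, within-woman SD or exit rate.

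**3. Reference cases.**
- Nobody lost, 20 v 20: noncentrality 8 / (7.55 × √(2/20)) = 3.35, power 90%, difference 8.0.
- Five Mix women lost at random, 20 v 15: noncentrality 8 / (7.55 × √(1/20 + 1/15)) = 3.10, power 85%, difference still 8.0.

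**4. Loss driven by the outcome.** Suppose k Mix women whose mean exceeds 90 are dropped with all their data. With a = (90 − μ − 8)/SD, such women lie on average E = SD × φ(a) / (1 − Φ(a)) above the Mix mean. The observed difference is then 8 − kE/(20 − k). For example, at μ = 80, a = 0.265 and E = 7.35. With k = 1 this gives 8 − 7.35/19 = 7.6, and with k = 5 it gives 8 − 5 × 7.35/15 = 5.55. Power comes from 100,000 simulated trials per setting, in which the women dropped are chosen at random from those above 90.

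| Control mean | E | k = 1 | k = 3 | k = 5 |
|---|---|---|---|---|
| 80 | 7.35 | 7.6; 87% | 6.7; 76% | 5.6; 59% |
| 82 | 6.02 | 7.7; 87% | 6.9; 77% | 6.0; 63% |
| 85 | 4.25 | 7.8; 88% | 7.2; 80% | 6.6; 69% |

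Each cell shows the observed difference in mg/dL, then power. At μ = 80 some simulated trials have fewer than five women above 90, so the simulated figure is 5.6 rather than 5.55.

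**5. Direction when pre-exit readings exist.** A weekly simulation used between-woman SD 7.55, within-woman SD 4 or 6, 8 or 12 weeks, the same control means, glucose falling by 0, 5 or 10 mg/dL over the first four weeks in both arms, and a true difference of 0 or 8. A Mix woman could exit at her third weekly value above 90, and about 3 to 5 of 20 did. There were 20,000 trials per setting.

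| Handling of women who exit | Bias, mg/dL (negative favours Mix) |
|---|---|
| Dropped entirely | −3.2 to −0.5 |
| Final readings only | −3.2 to −0.5 |
| All readings pooled | −1.6 to +0.1 |
| Pre-exit readings as per-woman means | +0.1 to +1.3 |
| Last reading carried forward | +0.3 to +2.0 |

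The sign depends on the handling, and the document does not fix the handling.

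**The case against.** **The loss is inferred.** It rests on women leaving the study plus silence on what follows. The sponsor may have meant only that the assigned insulin stops. Pre-meal and post-meal testing is the standard instruction, so fasting values may well continue on the meter as ordinary care. This stands: a reader might infer that follow-up is certainly lost, but the text shows only that the study makes no provision to collect it.

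**Data exist up to exit.** Meters are downloaded weekly, and A1C levels feed the same visits. Birth data are tied to enrolment. This also stands. A reader might infer that the exiting women's whole record, A1C included, disappears, and the document does not say so. What is unprovided for is fasting glucose after exit, and whether the end-of-protocol A1C is still taken.

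**Five exits is an adverse case.** It gives the Mix arm's whole 25% allowance for loss from any cause to this one clause, which is reached only after two treatment steps, and then discards all those women's data. With one to three exits the difference is 6.7 to 7.8 mg/dL and power 76% to 88%. A still stronger reading would remove every Mix woman whose mean exceeds 90. With no true difference, at SD 7.5 and means of 80, 85 and 90, that gives a bias of −1.4, −3.2 and −6.0 mg/dL and type I error of 8%, 26% and 61%. The protocol does not support it, because exit requires persistence through two evening steps and nothing says earlier readings are thrown away.

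**The 3 a.m. exit may pull the other way.** RATIONALE says "The potential downside to the premixed formulation is nocturnal hypoglycemia associated with the time lag between the dinner and breakfast dose", so that exit may also fall more often on the Mix arm. Its effect is unknown and is not netted here. A second selective loss would not restore comparability, but it adds to the doubt about direction.

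**Handling belongs to the analysis plan.** True of the choice among methods, and that plan is not shown. Whether data are collected after exit is a protocol matter.

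**Conclusion.** The point holds as a defect in what the protocol fixes about follow-up: one arm has an exit from the study triggered by the primary outcome, the other has none, and collection of fasting glucose and end-of-protocol A1C after exit is not provided for. This structural point needs no assumed numbers.

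Its size and direction are not established. The power and difference figures illustrate one handling, complete removal, over one to five exits, and rest on the back-solved SD and the assumed control means. A reader might infer that the bias must favour Mix. That is so when exiting women are dropped or only final readings are used, but per-woman means or carrying readings forward can reverse it.

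**What to change.** Leave the stopping criteria and clinical management as the sponsor has them. Add to METHODS that:

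- a woman who meets either discontinuation criterion, in either arm, remains in study follow-up;
- meter fasting glucose, hypoglycemia, end-of-protocol A1C and birth data are still collected to delivery;
- the primary comparison includes all randomised women in their assigned arm.

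Simply rewording the exit as stopping study insulin would not do. The same sentence carries the 3 a.m. ground, so the change would also alter a treatment-stopping statement for women on usual insulin.

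No extra patients are needed. The cost is some continued data collection. The comparison will also include time off the assigned regimen, which can shrink the contrast toward the equivalence the sponsor anticipates. If 5 of 20 Mix women exit and their 8 mg/dL excess then vanishes for a fraction f of the observed time, the difference becomes 8 − 8 × (5/20) × f: 7.5 mg/dL at f = 0.25 and 6.0 at f = 1. A supporting analysis of readings up to discontinuation would show how far this matters.

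### Adherence is measured by counting pens, with no stated link to the units prescribed, although doses change weekly and the arms differ in injections and products

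*Protocol*

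**What the plan says.** Secondary objective 4 is to "Compare adherence rates and patient acceptability of the two injection regimens". Methods gives the measure: "The insulin pens will be counted as measures of adherence". Secondary Efficacy Measures repeats it: "We will use insulin pen count data as an indicator of maternal adherence to the therapy regimen".

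Methods also fixes the conditions under which the count is taken:

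- Doses: "Participants will be seen weekly for adjustment in dosages based on their food records, downloaded glucose monitor data and A1 C levels".
- Timing of the count: "Participants will be asked to bring their supply of insulin pens to every other visit". With weekly visits, each count covers about 14 days and about two dose periods.
- Standard arm: six injections a day of two products ("Humalog® injected three times daily before meals plus Humulin N® insulin injected at 8am, 4pm and midnight").
- Mix arm: three premeal injections of one premix. If fasting glucose exceeds 90 mg/dL, a woman "will be prescribed Humalog® Mix75/25™ at their evening meal rather than Humalog® Mix50/50™", which brings in a second pen type.
- Starting doses: 0.3 x kg at each of three injections, or 0.15 x kg at each of six.

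The protocol does not set the count against the prescription, have residual insulin read, say how part-used pens are treated, or mention pen content or priming.

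**The concern.** Pen use is the insulin injected plus the insulin wasted. The insulin injected depends on what was prescribed as well as on how much of it was taken. When each woman's prescription moves weekly, a count not set against it cannot separate a woman who skipped doses from one whose dose was lower. Waste that occurs at each injection adds more in the six-injection arm. A count in whole pens may also be too coarse for modest non-adherence.

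At stake is the adherence part of secondary objective 4. The pen count is its only named measure, participants are paid to bring their pens in, and about 15 evaluable women per arm are planned. A difference in counts could arise without a difference in adherence, and a real difference could be hidden.

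**Working it through.** The protocol gives no adherence figure, so there is nothing to reproduce. The inputs from Methods are the starting dose factors, 6 v 3 injections a day, weekly dose changes and a 14-day count interval. Assumptions not in the protocol are body weight of 60 to 100 kg, priming waste of 0 to 3 units per injection and, where stated, 300-unit pens.

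**1. Starting dose by arm.** Mix: 3 x 0.3 = 0.9 x kg per day. Standard: 6 x 0.15 = 0.9 x kg per day. These are equal, so prescribed dose does not separate the arms at the start.

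**2. Dose against adherence (no pen size needed).** With six equal doses, one injection missed daily leaves 5/6 of the units. A 20% higher prescription restores them: 5/6 x 1.2 = 1.0, ignoring priming. One missed injection a day is 1/6 of units in the standard arm and 1/3 in the Mix arm at starting doses, so the same behaviour moves the count differently by arm.

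**3. Titration within one count interval.** If the dose rises by a fraction u in the second week, 14-day use is multiplied by (2 + u)/2, and adherence of 2/(2 + u) cancels the rise. The values of u are illustrative.

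- u = 10%: use +5%, hides adherence of 95%.
- u = 20%: use +10%, hides adherence of 91%.
- u = 30%: use +15%, hides adherence of 87%.

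**4. Waste per injection.** Full-adherence use over 14 days is 14 x (0.9 x kg + injections x prime). At 80 kg with a 2-unit prime, the standard arm uses 14 x (72 + 12) = 1176 units and the Mix arm 14 x (72 + 6) = 1092, a ratio of 1.077. Excess use in the standard arm at full adherence in both arms:

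| Prime (units) | 60 kg | 80 kg | 100 kg |
|---|---|---|---|
| 0 | 0% | 0% | 0% |
| 1 | 5.3% | 4.0% | 3.2% |
| 2 | 10.0% | 7.7% | 6.25% |
| 3 | 14.3% | 11.1% | 9.1% |

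**5. Coarseness of a whole-pen count.** The 14-day starting dose is 14 x 0.9 x kg: 756 units at 60 kg, 1008 at 80 kg and 1260 at 100 kg. One 300-unit pen is therefore 300/756 = 40% down to 300/1260 = 24% of it. For each standard-arm product, which carries half the dose, one pen is 79% down to 48%. Missing 10% of doses is 75.6/300 = 0.25 to 126/300 = 0.42 of a pen.

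One standard-arm injection missed every day is 14 x (0.15 x kg + prime)/300. At 80 kg with a 2-unit prime this is 14 x 14/300 = 0.65 of a pen. The range is 0.42 (60 kg, no prime) to 0.84 (100 kg, 3 units).

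This step depends on pen content. At 150 units, one pen would be 12% to 20% of the 14-day dose, and the 0.65 would become 196/150 = 1.3 pens.

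**The case against.** The strongest reply is that the protocol never says unadjusted counts will be compared. It calls the count an indicator, and objective 4 speaks of rates, which suggests a denominator. Deriving a secondary variable is normal business for an analysis plan, and one may exist. This stands in part: a reader might infer that raw counts are to be compared, but the text neither says nor excludes that. An analysis plan could add prescribed units as a denominator. It could not recover residual volumes that were never read at the visit. The data-collection rule sits in the protocol, and that rule is to count pens.

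A second reply is that pen use still falls when doses are skipped, and that both arms start on the same daily dose. Both statements are correct. A reader might conclude that the count measures dose and priming instead of adherence, or that the arms' doses differ from the outset. The protocol supports neither. Dose-related distortion arises only through later titration, and nothing in the document shows that the arms will titrate to different totals.

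Third, priming, pen content and body weight lie outside the document. That stands: the waste effect is zero if there is no priming. Repeated counts also lessen the coarseness. On the 0.65-pen figure, one missed injection a day adds up to about 2.6 pens over four intervals (4 x 0.65). Accumulation does not remove the mixing with dose.

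Finally, a reader might take this to undermine the study hypothesis. The hypothesis names ease of use, not adherence, and objective 4 also covers patient acceptability.

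**Conclusion.** The point holds as a defect in how a secondary measure is specified, and the measure should be changed. As written, the pen count mixes adherence with prescribed dose. This follows from the protocol's own weekly adjustment and every-other-visit count, and in the standard arm a 20% higher dose hides one missed injection in six whatever the pen size, ignoring priming. Two further effects rest on assumptions. Waste per injection makes fully adherent standard-arm use 0% to about 14% higher than in the Mix arm (0 to 3 units of priming, 60 to 100 kg). Whole-pen counting has a step of 24% to 40% of the 14-day starting dose (300-unit pens, same weights). Only the adherence comparison in secondary objective 4 is affected. The primary fasting-glucose comparison is not.

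**What to change.** In Methods and in Secondary Efficacy Measures, replace the pen count with a ratio for each count interval:

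- At the existing every-other-visit check, the coordinator reads the residual units in each pen.
- The site keeps a record of pens supplied and of each week's prescribed doses. The weekly adjustments imply that doses are known, but the protocol mentions no such record.
- Adherence = units used / units expected at full adherence, where expected = prescribed units + a stated waste allowance x prescribed injections. Compute it by product, sum over products, and compare the ratio between arms.

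The allowance belongs in the denominator. At 80 kg with a 2-unit prime, a standard-arm woman missing one injection in six uses 14 x 5 x 14 = 980 units. The ratio is 980/1176 = 83.3%, which is correct. Deducting a fixed allowance from the numerator would give (980 - 168)/1008 = 80.6%, because it charges waste for injections that were not given.

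The cost is a few minutes at each pen visit and simple record keeping. No visit is added and no treatment rule changes.
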